4.1.1.3 Primary Definition of Progression-Free Survival (PFS)

PFS will be primarily analyzed applying an intent-to-treat (ITT) definition that utilizes all of the data on each randomly assigned subject at the time of the PFS analysis. PFS will be defined as the time from randomization to the date of the first documented tumor progression or death due to any cause. Clinical deterioration will not be considered progression. A subject who neither progresses nor dies will be censored on the date of their last adequate tumor assessment. A subject who does not have any post-baseline tumor assessments and who has not died will be censored on the date of randomization.

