7.2.2 Protocol Violations

A relevant protocol deviation is defined as a deviation from the protocol which is programmed in the database and which could potentially affect the interpretability of the study results.

The number and percentage of subjects with any relevant protocol deviation and each specific deviation will be presented overall and by treatment group.

The following eligibility deviations are considered relevant in this study and will be summarized for all treated subjects:

- 1) Number of prior systemic anti-myeloma therapy is < 2
- 2) Non-measurable disease. This occurs when none of the following three conditions are met:
 - Serum IgG, IgA, or IgM M-protein $\geq 0.5\text{g/dL}$
 - M-protein $\geq 200\text{mg}$ in 24-hour urine
 - Involved serum free light chain (sFLC) $\geq 100\text{ mg/dL}$ provided the FLC ratio is abnormal
- 3) Ineligible for this study due to failure to meet criteria for refractory or relapsed and refractory MM. This occurs when:
 - Subjects did not progress (on or within 60 days of treatment) to their last treatment (not refractory).
 - Subjects did not fail treatment with a proteasome inhibitor and lenalidomide. This occurs when none of these take place:
 - i) “Refractory” to proteasome inhibitor and lenalidomide, and to their last treatment.
 - ii) “Relapsed and refractory” = patients had achieved at least a partial response to previous treatment with proteasome inhibitor or lenalidomide, or both, but progressed within 6 months, and were refractory to their last treatment.

Also, the following on-treatment deviations are considered relevant in this study and will be summarized for all treated subjects:

- 4) Non-protocol specified systemic anti-myeloma therapy prior to discontinuation of study therapy
- 5) Received non-assigned treatment regimen throughout the study
- 6) No baseline efficacy assessment. This occurs when there are no tumor assessments at all (laboratory assessments) on or prior to first day of dosing.
- 7) Subjects continuing to receive study therapy after 10 weeks of documented progression per investigator (as progression needs to be confirmed).

If assessments based on the central laboratory is unavailable, but the local laboratory results are available, then those will be used for evaluating deviations 2 and 6.

A by subject listing of relevant protocol deviations will be provided.

[REDACTED]

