7.5.1.1 Supportive Analyses of Progression-Free Survival

The following supportive analyses will be conducted using both the ITT and the secondary definitions of PFS. P-values provided for these analyses are descriptive and will be used to evaluate the results in context of the primary analyses.

- 1) A multivariate Cox regression model will be used in order to estimate the treatment effect after adjustment for possible imbalances in known or potential prognostic factors. The factors used in the randomization, which, by definition, will be balanced across arms, will still be included in the model as stratification factors. However, all additional factors will be incorporated as covariates. The additional factors, which are all measured at baseline, will include: age (< 75 vs. ≥ 75), gender (male vs. female), ECOG PS (0-1 vs. 2), prior stem cell transplantation (yes vs. no), high myeloma risk (yes vs. no) [see [Section 7.5.1.2](#) for details], time from initial diagnosis, creatinine clearance (<60ml/min vs. ≥ 60 ml/min), and LDH (< 300IU/L, ≥ 300 IU/L).

The level of the covariate normally associated with the worst prognosis will be coded as the reference level:

- Age: ≥ 75
- Gender: Female
- ECOG: 2
- Prior stem cell transplantation: Yes
- High myeloma risk: Yes
- Time from initial diagnosis (\geq median)
- Creatinine clearance: < 60 ml/min
- LDH (≥ 300 IU/L)

The p-value associated with treatment and with each of the baseline covariates will be presented. The hazard ratio along with the associated 95% CI will also be presented. In addition, an 80% CI will be provided for the treatment effect.

- 2) PFS using stratification factors as obtained from the baseline CRF pages (instead of IVRS). The p-value and the hazard ratio associated with treatment will be presented along with the associated 2-sided 80% and 95% CIs. This analysis will be performed only if there is a difference of 10% in strata between the IVRS and CRF pages.
- 3) PFS using an un-stratified log rank test. The p-value and hazard ratio associated with treatment will be presented along with its associated two-sided 80% and 95% CIs.
- 4) PFS using an unstratified Cox proportional hazards model, adjusted, using as covariates only the two stratification factors used in randomization. The p-value and hazard ratio associated with treatment will be presented along with its associated two-sided 80% and 95% CIs.

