- 5) PFS for subjects with no relevant deviation. These analyses will be conducted only if there are more than 5% subjects with relevant protocol deviations. The p-value and hazard ratio associated with treatment will be presented along with its associated two-sided 80% and 95% CIs.

A by-subject listing will be presented including treatment arm, PFS duration under the primary definition, PFS duration under the secondary definition, whether the subject was censored under the primary definition, and if censored, the reason, and whether the subject was censored under the secondary definition, and if censored, the reason.

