7.5.3 Analysis of Overall Survival

Overall survival is another secondary objective. It will be compared between arms using a stratified log-rank test procedure with a two-sided, $\alpha = 0.2$ level. The stratification factors will be the same as those used for the analyses of PFS and tumor response. The OS function for each randomized arm will be estimated using the Kaplan-Meier product-limit method. Median and two-sided 95% confidence intervals for median OS will be computed by randomized arm.

All analyses performed for PFS (detailed in [Section 7.5.1](#)) will be repeated for OS. Supportive analyses of PFS (detailed in [Section 7.5.1.1](#)) as well as the subset analyses (detailed in [Section 7.5.1.2](#)) will also be repeated for OS.

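### The no-deviation PFS and OS analyses exclude subjects treated more than 10 weeks past progression, so the analysis set depends on the outcome

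*SAP*

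**What the plan says.** SAP 7.2.2 divides relevant deviations into eligibility deviations (1 to 3) and a second group (4 to 7), introduced by "the following on-treatment deviations are considered relevant in this study and will be summarized for all treated subjects". Deviation 7 is "Subjects continuing to receive study therapy after 10 weeks of documented progression per investigator (as progression needs to be confirmed").

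SAP 7.5.1.1 item 5 is "PFS for subjects with no relevant deviation". It exempts none of the seven. It has a trigger: "These analyses will be conducted only if there are more than 5% subjects with relevant protocol deviations". The section preamble adds "The following supportive analyses will be conducted using both the ITT and the secondary definitions of PFS", and on their status, "P-values provided for these analyses are descriptive and will be used to evaluate the results in context of the primary analyses". SAP 7.5.3 says that the supportive PFS analyses "will also be repeated for OS".

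The PFS event itself is set in SAP 4.1.1.3: "PFS will be defined as the time from randomization to the date of the first documented tumor progression or death due to any cause". SAP 7.5 and 7.5.1 base the primary comparison on all randomized subjects, grouped as randomized.

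**The concern.** A no-deviation analysis is meant to show whether the primary result survives when subjects who departed from the protocol are set aside. That works when the departure is fixed before the outcome, as with the eligibility deviations. Deviation 7 is different: it cannot exist until the PFS event has occurred.

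The hazard ratio is distorted mainly if the deviation is more frequent in one arm, and the protocol gives reasons not to presume equal rates. The trial is open-label and PFS is investigator-assessed. Protocol 3.5 makes stopping at progression mandatory for investigational product and leaves non-investigational product to the investigator. Under Protocol 4.1 and 4.2 only elotuzumab is investigational, so the whole control regimen falls under that discretion. Protocol 4.5.3 counts a subject on pomalidomide or dexamethasone alone as still on study therapy. The direction of any imbalance cannot be read from the documents. At stake is a check that could falsely reassure or falsely alarm.

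**Working it through.** **1. Who can be removed.** To meet deviation 7 a subject must (a) have a documented progression, (b) live at least 10 more weeks, and (c) still be on study therapy then.
- Primary PFS: (a) is the event, so every subject removed has an event. Progressions less than 10 weeks before cut-off cannot be flagged, so earlier events are removed preferentially.
- Secondary PFS (SAP 4.1.1.4): a progression more than 10 weeks after the last adequate assessment is censored. A few of those removed may therefore be censored; nearly all should have events.
- OS: everyone removed has survived at least 10 weeks past progression. The selection is on survival time, so the bias runs the other way.

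**2. The trigger.** 5% of 114 is 0.05 × 114 = 5.7, so 6 subjects suffice if the denominator is 114. Deviation 7 counts towards this and can itself cause the analysis to run.

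**3. The plan's own figures** (SAP 5.1 and 5.3), assuming 1:1 allocation because the ratio is not visible. With z(0.90) = 1.2816 and z(0.85) = 1.0364:
- Schoenfeld events: 4 × (1.2816 + 1.0364)² / (ln 0.57)² = 21.49 / 0.316 = 68.02, rounded up to 69.
- Freedman events: (1.57 / 0.43)² × 5.373 = 71.6, rounded up to 72. The plan states 71.
- Power with 71 events at HR 0.57: 86.1% (plan 85%). Power with 78 deaths at HR 0.64: 75.5% (plan 75%).

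**4. PFS simulation.** From the SAP: 114 subjects, control median 4.0 months, about 9 months' accrual, cut-off at 71 events, two-sided α = 0.2, true HR 1.00 or 0.57. Assumed: exponential times, 90% of events are progressions, and a given share per arm of progressors with more than 10 weeks left before cut-off is treated on and dropped. Test: unstratified log-rank, 4,000 trials per row.

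| True HR | Share treated on, Pd / E-Pd | Mean dropped | HR, all subjects | HR, no-deviation set | Rejection, all → no-deviation |
|---|---|---|---|---|---|
| 1.00 | 20% / 20% | 8.9 | 1.01 | 1.01 | 20.6% → 20.8% |
| 1.00 | 0% / 20% | 4.5 | 1.00 | 0.92 | 20.0% → 22.1% |
| 1.00 | 10% / 30% | 8.9 | 1.01 | 0.92 | 19.8% → 22.3% |
| 1.00 | 5% / 35% | 9.0 | 1.00 | 0.87 | 19.9% → 26.8% |
| 1.00 | 30% / 10% | 8.9 | 0.99 | 1.10 | 19.6% → 21.6% |
| 0.57 | 20% / 20% | 10.0 | 0.57 | 0.56 | 84.8% → 82.6% |
| 0.57 | 10% / 30% | 9.0 | 0.57 | 0.50 | 85.1% → 91.7% |
| 0.57 | 30% / 10% | 10.7 | 0.57 | 0.62 | 85.6% → 71.0% |

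With nobody dropped, the simulation returns HR 1.00 with 19.9% rejection and HR 0.57 with 84.9% power, as it should. Under no effect at 10% / 30%, false results favouring E-Pd rise from a nominal 10% to 17%. Equal 20% rates leave the HR alone but lengthen the medians: under no effect, from 4.0-4.1 to 4.4-4.5 months.

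**5. Variants.** With 15% of events as deaths, the null HR becomes 0.91 or 1.10. Also requiring 10 weeks' survival after progression (assumed median post-progression survival 10.5 months) gives 0.93 or 1.08, and 0.57 becomes 0.51 or 0.61. At lower rates of 5% / 10%, 1.00 becomes 0.98 and 0.57 becomes 0.55, with about 3 subjects flagged.

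**6. OS.** Cut-off at 78 deaths, no true effect, the same post-progression assumption. At 10% / 30% the HR becomes 1.06, at 0% / 20% 1.05, and at 30% / 10% about 0.94. Equal 20% rates shorten the pooled median from 15.4 to 14.6 months. That simulated median exceeds the 12.7 months planned for Pd, so the OS figures show direction and rough size only.

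**The case against.** **Little rests on this analysis.** It is one of five supportive analyses, its p-values are descriptive, it runs only above the 5% trigger, and the topline list in SAP 8.7 does not name it. This stands. The change in rejection rate is therefore not a loss of power for the trial, because no decision uses this test.

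**The size comes from assumed rates.** This also stands. The larger shifts need about 30% of eligible progressors in one arm to be treated on, three times the other arm. At 5% / 10%, deviation 7 alone passes the trigger in only about 10% of simulated trials; at 10% in both arms, in 24-33%. The shifts are also small against sampling error. At 10% / 30%, PFS under no effect moves by |ln 0.92| / (2/√71) = 0.083 / 0.237 = 0.35 standard errors, and from 0.57 to 0.50 by 0.131 / 0.237 = 0.55. OS moves by ln 1.06 / (2/√78) = 0.058 / 0.226 = 0.26. But the defect in the rule needs no particular rate, and SAP 7.5.1.1 says that these results will be used to interpret the primary one.

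**Staying on study drug past progression is a compliance matter.** A reader might infer that deviation 7 has nothing to do with compliance. The documents do not support that: the protocol synopsis continues treatment until progression, and Protocol 3.5 lists progression as a reason to stop investigational product. Tabulating it as a relevant deviation is sound. Only its use as an exclusion is at fault.

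**Deviation 4 also occurs after randomization.** A reader might infer that it can be dropped too, because the secondary PFS definition censors at new therapy. That does not carry over: neither primary PFS (SAP 4.1.1.3) nor OS (SAP 4.1.3) has such censoring. Deviation 4 also does not require a prior event.

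**Conclusion.** The point holds, with limited reach. As written, item 5 selects subjects on the outcome for PFS under both definitions and for OS. That follows from the text alone. Its effect on the HR depends on assumed rates: negligible when the rates are equal or low, and a shift of roughly 0.07 to 0.10 in a null PFS HR at 10% against 30%, in either direction, with OS moving the opposite way by about 0.06.

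Two stronger readings should be resisted. A reader might infer that the trial's main PFS result is biased; it is not, because the primary analysis keeps all randomized subjects. A reader might also infer that the exclusion never removes a censored subject; that is exact only for the primary PFS definition.

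The change is worth making because it is cheap and removes a bias created by the rule itself.

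**What to change.** Add one sentence to SAP 7.5.1.1 item 5: deviation 7 is not used to exclude subjects, and does not count towards the 5% trigger, for PFS under either definition or for the OS repeat in 7.5.3. Keep deviation 7 in the deviation table and the by-subject listing. Leave deviation 4 as it is, and do not justify any change to it by the censoring in the secondary PFS definition.

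No data collection, sample size, primary analysis or treatment rule changes. The one downside is that the analysis may be triggered less often.

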7.3.2 Demographic and Subject Characteristics

Demographic and baseline characteristics will be summarized, overall and by treatment group. The following parameters will be summarized; age at the time of informed consent (years), age category at time of informed consent (< 65 years, ≥ 65 years), and (< 75 years, ≥ 75 years), gender (Male, Female), race (White, Black/African American, American Indian/Alaska Native, Asian, Native Hawaiian/Other Pacific Islander, Other), ethnicity – for US subjects only (Hispanic/Latino, Not Hispanic/Latino), weight (kg), and ECOG performance status (0, 1, 2).

An accompanying by-subject listing of demographic and subject characteristics will be presented.

7.3.3 Disease Characteristics at Baseline

Baseline disease characteristics will be summarized, overall and by treatment group. The following parameters will be presented to summarize baseline disease:

- Serum M-protein (g/L)

- Urine M-protein (g/24 hours)
- Serum free light chain (g/L)
- Myeloma type (IgG, IgA, IgM, Light chain disease)
- Number of lytic bone lesions (0, 1-3, >3)
- Myeloma risk category
 - High risk: ISS stage II or III **and** t(4;14) or del(17p) abnormality
 - Low risk: ISS stage I or II **and** absence of t(4;14), del(17p) and 1q21 abnormalities and age < 55 years
 - Standard risk: any subjects not meeting the definition of high or low risk.
 - Not Evaluable: Subjects with missing data preventing their classification in the other 3 categories
- Individual FISH abnormalities (del 17p, t(14; 16), t(4; 14), del(1q), and del(1p))
- $\beta 2$ microglobulin (mg/L) (<3.5, ≥ 3.5 -5.5, ≥ 5.5)
- Albumin (g/L) (<3.5, ≥ 3.5)
- LDH (<300 IU/L, ≥ 300 IU/L)
- Soft tissue plasmacytomas (Yes, No)
- Refractory Status to prior lines of therapy:
 - Refractory to lenalidomide
 - Relapsed and refractory to lenalidomide
 - Refractory to proteasome inhibitor (PI)
 - Relapsed and refractory to proteasome inhibitor (PI)
 - Refractory to both PI and lenalidomide
 - Relapsed and refractory to both PI and lenalidomide
- ISS Stage (I, II, III) at enrollment and at diagnosis
- Time from disease diagnosis to randomization (months)

An accompanying by-subject listing of disease characteristics at baseline will be presented. All reports will be presented in standard international (SI) units and summaries in US units will also be available.

7.3.4 Prior Anti-Myeloma Therapy

Prior systemic anti-myeloma therapy (which will be identified from the eCRF page “Prior Therapy for Multiple Myeloma”) will be categorized using the WHO drug dictionary and will be summarized overall and by treatment group. The latest version of the drug dictionary at the time of the analysis will be used. The number and percentage of subjects with any prior systemic anti-myeloma therapy, the number and percentage of subjects who have received exactly 2, 3, and

≥4 prior lines of therapy, and the number of subjects receiving each therapy (generic term) will be presented.

A summary of the number and percentage of subjects receiving prior stem cell transplantation and prior radiotherapy will be presented overall and by treatment group.

A summary of the number and percentage of subjects receiving prior surgery related to cancer and each type of surgery (Kyphoplasty, Orthopedic surgery, Debulking surgery or Other) will be presented overall and by treatment group.

A by-subject listing containing relevant information on prior radiotherapy, prior surgery and prior systemic anti-myeloma therapy will be provided.

7.3.5 General Medical History

The number and percentage of subjects with any relevant medical history and by body system will be presented, overall and by treatment group.

By subject listings of medical history will be provided. A by subject listing of pregnancy test data will also be provided.

7.3.6 Baseline Safety Laboratory Tests

Baseline safety laboratory evaluations will be the last available samples taken on or before Cycle 1, Day 1 and within 60 days of randomization.

Baseline safety laboratory values (both SI and US units) will be presented by CTC severity grade, by treatment group. Separate tables will be generated for hematology (hemoglobin, WBC, ANC [neutrophils plus bands], ALC [absolute lymphocyte count] and platelets [neutrophils plus bands]), liver function (ALT, AST, alkaline phosphatase, albumin and total bilirubin) and renal function/electrolytes (sodium, potassium, bicarbonate, calcium, glucose, and creatinine, creatinine clearance < 60ml/min, ≥ 60ml/min). Sodium, potassium, calcium, and random glucose will be presented separately, based on their high and low values.

CTC grades will be derived as part of the analysis data set programming using version 3.0.

7.4 Extent of Exposure

7.4.1 Study Therapy

Pomalidomide, oral dexamethasone and IV dexamethasone are given at fixed doses and are not adjusted for body surface area or weight. The elotuzumab dose, in contrast, is adjusted for weight. Throughout this SAP, a subject's elotuzumab dose level at a particular time point will refer to the actual dose, in mg/kg, rather than their planned dose. A subject's actual elotuzumab dose level will be computed by dividing their total dose delivered, in mg, as recorded on the Record of Study Medication - Elotuzumab eCRF page, by their latest pre-dose weight, in kg, on Day 1 of that cycle.

7.4.1.1 Duration of Study Therapy

The number of cycles of treatment received by subjects will be summarized (using n, mean, STD, median, min, max, q1 and q3) by treatment group. A summary of the number of subjects taking each drug in each cycle will also be presented by treatment group.

The duration of each treatment (elotuzumab, dexamethasone [oral and IV combined] and pomalidomide), in months, will be calculated as:

$$(date\ of\ last\ dose\ of\ the\ drug - date\ of\ first\ dose\ of\ the\ drug + 1) / 30.4375$$

Duration of each of the study treatments will be summarized by treatment group.

7.4.2 Dose Modifications

7.4.2.1 Elotuzumab Dose Reduction

Reduction of elotuzumab dosing is not permitted as per the protocol.

7.4.2.2 Elotuzumab Dose Delay

A delay for elotuzumab will be computed based on records from the dosing CRF page. A delay in elotuzumab dosing will be defined as the number of days from the start date of the previous infusion to the start date of the current infusion being > 8 days and ≤10 days (if in cycles 1, 2 or cycle 3) or > 29 days and ≤ 35 days (from cycle 3 - onwards).

For courses with a delay of elotuzumab infusion, the time of delay in infusion will be summarized in the categories: 2-3 days, 4-7 days.

The number and percentage of subjects with any dose delay, with 1, 2, 3, or ≥ 4 reported delays will be summarized. For subjects with a delay, their reason for delay (from the dose modification page of the CRF) will be summarized in the groups: “hematologic toxicity”, “non-hematologic toxicity”, “AE”, “dosing error” and “other”. For subjects without an available reason for delay, the category “unknown” will be used.

7.4.2.3 Elotuzumab Dose Omission

An omission for elotuzumab will be calculated based on records from the dosing CRF page. If the interval between the two dosing dates for elotuzumab is > 10 days (in cycles 1, 2 or cycle 3) or > 35 days (from cycle 3 onwards), the dose will be considered to have been omitted.

For courses with an omission of elotuzumab infusion, the time between the previous and current infusion will be summarized in the categories: < 11 - 14, 15 - 21, 22-35, > 35 days.

The number and percentage of subjects with a dose omission, and with 1, 2, 3, or ≥ 4 omissions will be summarized. For subjects with an omission, their reason for omission (from the dose modification page of the CRF) will be summarized in the groups: “hematologic toxicity”, “non-hematologic toxicity”, “AE”, “dosing error” and “other”. For subjects without an available reason for omission, the category “unknown” will be used.

A by-subject listing for dose delay and omission will be presented for all treated subjects. This listing will include all reported delays or omission per CRF, regardless of whether the subject had a computed delay or omission based on the actual dosing dates.

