Protocol Title: An Open Label, Randomized Phase 2 Trial of Pomalidomide/Dexamethasone With or Without Elotuzumab in relapsed and refractory Multiple Myeloma

Investigational Product(s), Dose and Mode of Administration, Duration of Treatment with Investigational Product(s):

See **Study Schema** for details

Control Arm

Pomalidomide: 4 mg PO QD Days 1-21 of each cycle

Dexamethasone:

- Subjects \leq 75 years old: 40 mg PO Days (1, 8, 15 and 22) of each cycle
- Subjects $>$ 75 years old: 20 mg PO Days (1, 8, 15 and 22) of each cycle

Elotuzumab Arm

Elotuzumab:

- Cycle 1 - 2: 10 mg/kg IV Days 1, 8, 15 and 22 of each cycle
- Cycle 3 and beyond: 20mg/kg IV Day 1 of each cycle

Pomalidomide: 4 mg PO QD Days 1-21 of each cycle

Dexamethasone: Days 1, 8, 15 and 22 of each cycle

- Subjects \leq 75 years old: weeks with elotuzumab dosing: 28 mg PO + 8 mg IV and 40 mg PO on non-elotuzumab dosing weeks
- Subjects $>$ 75 years old: weeks with elotuzumab dosing: 8 mg PO + 8 mg IV and 20 mg PO on non-elotuzumab dosing weeks

A cycle is defined as 28 days. Treatment with study drug continues until disease progression, unacceptable toxicity (adverse event related to study drug), or subject meets other criteria for discontinuation of study drug outlined in [Section 3.5](#).

Study Phase: 2

[figure not shown]
Primary Objective:

- To compare progression free survival (PFS) between treatment arms

Secondary Objectives:

- To compare objective response rate between treatment arms
- To compare overall survival between treatment arms

Study Schema

Study Population:

Subjects who are diagnosed with relapsed and refractory multiple myeloma defined as:

- 1) Must have received ≥ 2 prior lines of therapy (See [Appendix 1](#)) which must have included at least 2 consecutive cycles of lenalidomide and a proteasome inhibitor alone or in combination.
- 2) Documented refractory or relapsed and refractory (R/R) multiple myeloma
- 3) Refractory (progressed on or within 60 days of treatment) to their last treatment.
- 4) Subjects must have failed treatment with a proteasome inhibitor and lenalidomide in one of the following ways.
 - a) “Refractory” to proteasome inhibitor and lenalidomide, and to their last treatment.
 - b) “Relapsed and refractory”= patients had achieved at least a partial response to previous treatment with proteasome inhibitor or lenalidomide, or both, but progressed within 6 months, and were refractory to their last treatment

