4.5.3 Dose Delay, Interruption, or Discontinuation, All Subjects

If the dose of one drug in the regimen (ie, pomalidomide, dexamethasone, or elotuzumab) is delayed, interrupted, or discontinued, the treatment with the other drugs may continue as scheduled. However, if dexamethasone is delayed or discontinued discuss ongoing elotuzumab administration with the medical monitor. Also see [Section 3.5](#) for delays in study drugs.

Each cycle is 28 days. While dose delays or interruptions are permitted, the start of each cycle cannot be delayed and is fixed (ie, anchored) relative to Cycle 1 Day 1. Adjustments to the Cycle 1 Day 1 anchored schedule should not be performed. Should the start of a cycle be delayed, it is expected the following cycle begin as anchored to Cycle 1 Day 1. For example, if a subject is unable to start Cycle (X) until 3 days after the anchored start date, all assessments should be recorded on Cycle (X) Day 3. The following cycle should begin on Day 1 (not Day 3) of Cycle (X+1). Missed doses should be skipped, not delayed, if not given within the allowed window.

Subjects may continue on study therapy even if components of the study therapy must be discontinued. For example, a subject on pomalidomide and dexamethasone may continue on study therapy even if dexamethasone must be discontinued for an adverse event. Likewise, a subject on the elotuzumab arm may continue on study therapy if elotuzumab must be discontinued for an adverse event or other reason. Subjects are considered still on study therapy even if they continue solely on pomalidomide or dexamethasone.

Please consult the BMS Medical Monitor or any questions regarding dose interruption or study

Subjects should be instructed that if a dose of pomalidomide has been missed and it has been less than 12 hours since the subject’s regular dosing time, to take pomalidomide as soon as the subject remembers. If it has been more than 12 hours, the dose must be skipped. Subjects should not take 2 doses at the same time

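### The elotuzumab delay and omission rules put cycle 3 under both the weekly and the 4-weekly limits and do not say which infusion's cycle selects the limit

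*SAP*

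**What the plan says.** The schedule is in the Protocol synopsis, Elotuzumab Arm: "Cycle 1 - 2: 10 mg/kg IV Days 1, 8, 15 and 22 of each cycle", and after that a 4-weekly schedule, "Cycle 3 and beyond: 20mg/kg IV Day 1 of each cycle". The synopsis adds "A cycle is defined as 28 days", and Protocol 4.5.3 says that "the start of each cycle cannot be delayed and is fixed (ie, anchored) relative to Cycle 1 Day 1".

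SAP 7.4.2.2 counts the days between the start of one infusion and the start of the next. Its weekly limb calls the infusion delayed when that count is "> 8 days and ≤10 days (if in cycles 1, 2 or cycle 3". Its 4-weekly limb, given as an alternative, uses a longer range: "> 29 days and ≤ 35 days (from cycle 3 - onwards". For omissions, SAP 7.4.2.3 flags a dose when the time between two infusions "is > 10 days (in cycles 1, 2 or cycle 3) or > 35 days (from cycle 3 onwards".

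Both rules therefore name cycle 3 twice, once under the weekly limits and once under the 4-weekly limits, joined by an or. Both are calculated from the dosing CRF records. SAP 8.7 lists both resulting summaries among the topline exposure outputs.

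**The concern.** Every interval has two ends, and around cycle 3 the two ends can lie in cycles with different schedules. The planned interval into Cycle 3 Day 1 is weekly and the planned interval out of it is 4-weekly. A rule that says only that an interval is in cycle 3 does not tell the programmer which of the two is meant, and the overlap means that both limits can be applied to the same interval.

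What is at stake is the description of exposure to the only investigational product in the trial. Depending on the choice made in programming, a correctly timed infusion could be reported as an omission, one gap could appear in both tables, or a truly missed dose could be reported as a delay. Where no CRF reason matches the computed event, the SAP places it in the category for unknown reasons, so the tables could look complete while being wrong.

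**Working it through.** **Inputs.** Cycle length 28 days; infusions on Days 1, 8, 15 and 22 of Cycles 1 and 2, then on Day 1 only (Protocol synopsis); cycle starts anchored to Cycle 1 Day 1 (Protocol 4.5.3); limits of 8, 10, 29 and 35 days (SAP 7.4.2.2 and 7.4.2.3). CxDy below means Cycle x Day y.

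**The SAP's own figures.** Delay = interval − planned interval. On the weekly limb, 9 − 7 = 2 and 10 − 7 = 3 days. On the 4-weekly limb, 30 − 28 = 2 up to 35 − 28 = 7 days. These reproduce the delay categories in SAP 7.4.2.2 (2-3 and 4-7 days), so the limits themselves are coherent. The difficulty is only which limit applies.

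**Study days.** Day = 28 × (cycle − 1) + day in cycle. C1D22 = 22; C2D22 = 28 + 22 = 50; C3D1 = 56 + 1 = 57; C4D1 = 84 + 1 = 85.

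**The written rules, applied both ways, and the corrected rule** (limit selected by the previous infusion; weekly for Cycles 1-2, 4-weekly from Cycle 3):

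| Interval | Days | Written rule, previous infusion selects | Written rule, current infusion selects | Corrected rule |
|---|---|---|---|---|
| C2D22 to C3D1, on time | 57 − 50 = 7 | neither | neither | neither |
| C3D1 to C4D1, on time | 85 − 57 = 28 | omission (28 > 10) | neither (28 ≤ 29) | neither |
| C1D22 to C3D1, all Cycle 2 doses missed | 57 − 22 = 35 | omission | omission (35 > 10) and delay (29 < 35 ≤ 35) | omission |
| C2D22 to C4D1, C3D1 missed | 85 − 50 = 35 | omission | delay only (29 < 35 ≤ 35; not > 35) | omission |

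**Previous infusion selects.** The 28-day interval starts in cycle 3, so the weekly limb applies and flags it. It would be tabulated in the omission category of 22-35 days.

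**Current infusion selects.** For an interval ending at C3D1, 9-10 days is a delay and 11-29 days is an omission by the weekly limb; the 4-weekly limb adds nothing. At 30-35 days the weekly limb gives an omission and the 4-weekly limb gives a delay, so the gap is counted twice. In the last row of the table, C4D1 is given on its anchored day, yet it is reported as 35 − 28 = 7 days late and the missed C3D1 dose is not reported as omitted. That case sits on the boundary: if C4D1 were one day later the interval would be 36 days and would count as an omission.

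**Whole schedule.** For a subject infused on time from C1D1 to C6D1, the corrected rule gives 0 delays and 0 omissions.

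**The case against.** The intended rule can be guessed. SAP 7.4.2.2 mentions the current infusion immediately before the condition "if in cycles 1, 2 or cycle 3", and SAP 7.4.2.3 tabulates the time from the previous to the current infusion. Read that way, the interval from C3D1 to C4D1 belongs to cycle 4 and is not flagged. Cycle 3 also has an evident reason to appear in the weekly limb, since C3D1 is planned 7 days after C2D22; no 7-day interval starts in cycle 3. This stands: a reader might infer that every subject reaching Cycle 4 on time would be shown with an omission, but that needs the less natural assignment, and the documents do not establish it.

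A reader might also infer that one of the two limbs must be wrong on any reading. That too goes further than the text. A mixed convention, with weekly limits for intervals ending by C3D1 and 4-weekly limits for intervals starting at C3D1 or later, classifies the on-time schedule correctly. But the SAP does not state it, it gives cycle 3 two meanings in one sentence, and it leaves the interval from C2D22 to C4D1 under neither limb, because that interval starts before cycle 3 and ends after it.

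The double count is also rare. A gap of 30-35 days before an on-time C3D1 (day 57) means a last infusion on days 22-27, with all four Cycle 2 infusions missed; otherwise it needs several missed doses and a late Cycle 3 dose as well. Finally, the by-subject listing in SAP 7.4.2.3 shows CRF-reported delays and omissions regardless of the computed result, and SAP 8.7 lists dose intensity separately. These points limit the harm but do not supply the missing rule.

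**Conclusion.** The point holds as an ambiguity with specific misclassifications, and it is minor. Cycle 3 is under both limits in both sections, and the infusion that selects the limit is not stated. On the less natural reading an on-time 28-day interval can be counted as an omission. On the more natural reading that interval is correct, but a 30-35 day gap ending at C3D1 is both a delay and an omission, and a single missed C3D1 dose with its neighbours on time is a delay and not an omission.

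The examples assume that the infusions actually given fall on their anchored days. The documents contain no dosing data, so no count or percentage of affected subjects can be given. The effect is confined to the descriptive elotuzumab delay and omission summaries. No test or estimate of PFS, ORR or OS depends on them. The point concerns how intervals are classified for analysis and says nothing about the dosing schedule.

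**What to change.** In SAP 7.4.2.2 and 7.4.2.3, state that the limit is selected by the cycle of the previous infusion, and make the ranges non-overlapping:

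- previous infusion in Cycles 1-2: delay if the interval is > 8 and ≤ 10 days, omission if > 10 days;
- previous infusion in Cycle 3 or later: delay if > 29 and ≤ 35 days, omission if > 35 days.

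Changing cycle 3 to cycle 4 in the 4-weekly limb is not enough. With the current infusion selecting the limit, it removes the double count but still reports a missed C3D1 dose as a delay. If the previous infusion is used instead, it leaves the on-time 28-day interval under the weekly limit alone, so the false omission becomes certain.

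The cost is a few words in two sections and the matching line in the programming specification. The numerical limits, delay categories and data collected stay as they are.
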